11 STATISTICAL CONSIDERATIONS

11.1 Statistical design, method and analytical procedures

Exploratory data analysis will be used to describe the patient population.

11.2 Sample size

For this study, no statistical hypotheses can be formulated; therefore a sample size calculation is not applicable. However, at least six patients for each condition (see section 4.2) should be enrolled for the following reasons:

A minimum sample size of six would be needed to draw a conclusion with inferential statistics from binary data; e.g. to successfully apply a new algorithm in all 6 samples, a random effect can be excluded based on a 5 % significance level with an exact 95 % confidence interval larger than 50 %. Since ventricular tachycardia is most important in the development of certain detection algorithms, a minimum of ten patients is foreseen. Thus, in case of a successful application of a new algorithm in 10 of 12 samples, a random effect can be excluded based on a 5 % significance level. Consequently, $13 \times 6 + 12 = 90$ patients should be at least enrolled. Due to an assumed rate of 10 % non-evaluable ECG recordings, at least 100 patients should be enrolled in the study. However, due to the conditions defined for replacements of patients (section 8.1.4) and a potential time delay in ECG analysis by the sponsor (section 8.1.3.3), the total number of enrolled patients might exceed the planned sample size.

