2 SYNOPSIS

Title	Collection of ECG signals from various patient groups for the development of algorithms for sensing and detection of rhythm anomalies
Patient population	Patients from the investigator's general collective and with different forms of diagnosed arrhythmias and/or specific ECG characteristics from heart diseases as listed in the inclusion criteria.
Design	Prospective, multicenter, non-randomized, interventional
Objectives	Collect data from surface ECGs by using Holter ECG recordings from patients with different forms of diagnosed arrhythmias and/or specific ECG characteristics from heart diseases to support the development of new sensing and detection algorithms for implants.
Endpoints	Number of successful ECG recordings per condition
Additional Data of Interest	
 Demographic data, medical history, ECG diagnosis Adverse Events related to the study procedure Optional: chest x-ray, only if available and part of a procedure prior to enrollment
Inclusion criteria	
 Patient is able to understand the nature of the study and willing to provide written informed consent Patient is willing and able to attend Holter ECG procedure following a visit History of at least one of the following conditions (established via ECG prior to enrollment): 
 (A) Patient with pacemaker/ICD and 
 Ventricular stimulation > 30 % or (B) Patient either without pacemaker/ICD, or with pacemaker/ICD but without significant atrial and ventricular stimulation, and at least one of the following: 
 Frequent Ventricular Extrasystoles (VES) (incl. Bigeminus) or Atrioventricular Reentrant Tachycardia (AVRT)/ Wolff-Parkinson-White (WPW) syndrome or Atrioventricular Nodal Reentrant Tachycardia (AVNRT) or Sinus Tachycardia at rest or Atrial Flutter or Any form of Ventricular Tachycardia (VT) or Silent/paroxysmal/persistent/permanent AF or Brugada syndrome or Long QT syndrome or Right Bundle Branch Block (RBBB) or

	12. Left Bundle Branch Block (LBBB) or
	13. Myocardial Ischemia/Acute Myocardial Infarction or
	14. Other abnormal QRS(T) complex, ST segment or T-wave morphology, i.e. any other
	
 ○ QRS anomaly ○ ST segment elevation ○ ST segment depression ○ T wave changes

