7.2 Endpoints and hypotheses

As described in section 11.2, the number of successful ECGs per condition stated in the inclusion criteria (section 8.3.2) was chosen as an endpoint, whereat each condition shall be included at least six times and at most ten times; with the exception of 'Any form of Ventricular Tachycardia (VT)' being included at least twelve times or more.

There are no predefined hypotheses.

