8.1.3.3 Allocation of patients to a subgroup by the sponsor

As stated in section 7.2, at least 6 but no more than 10 patients shall be included for each subgroup which defined in the inclusion criteria (section 8.3.2), the exception being 'Any form of Ventricular Tachycardia (VT)' which shall be included at least 10 times or more.

A first allocation of the patient to one or more subgroups will be done by the investigator by completing the enrollment CRF.

A subsequent allocation to a single subgroup will be done internally after the evaluation of the ECG recording by the sponsor's research and development department. After reaching the desired number in one of the subgroups, the sponsor will announce its closure to the participating investigators and data entry will be restricted for patients who are allocated only to this single subgroup.

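### The minimum number of ventricular tachycardia patients is twelve in some places of the protocol and ten in others

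*Protocol*

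**What the plan says.** The synopsis names one endpoint: "Number of successful ECG recordings per condition". Protocol 7.2 gives each condition a range of six to ten, with VT as the exception, "being included at least twelve times or more". It refers to the sample size section for the basis: "As described in section 11.2, the number of successful ECGs per condition stated in the inclusion criteria". SAP chapter 10 reproduces this text as an excerpt of 7.2.

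Protocol 8.1.3.3, on allocating patients to subgroups, opens with "As stated in section 7.2, at least 6 but no more than 10 patients shall be included for each subgroup" and again makes VT the exception, but as a condition "which shall be included at least 10 times or more".

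Protocol 11.2 contains both numbers. Its prose reads "Since ventricular tachycardia is most important in the development of certain detection algorithms, a minimum of ten patients is foreseen". The following sentence says that, "in case of a successful application of a new algorithm in 10 of 12 samples, a random effect can be excluded" at the 5 % level. The formula after that is 13 × 6 + 12 = 90 patients as the minimum, raised to 100 for an assumed 10 % of non-evaluable recordings.

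**The concern.** The VT minimum is the stated target of the study's only endpoint, for the condition that 11.2 singles out as most important for certain detection algorithms. It is given as twelve in 7.2, in the rule of 11.2 and in the formula of 11.2, and as ten in 8.1.3.3 and in the prose of 11.2. A reader who follows the references cannot tell which applies.

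Two things are at stake. First, 8.1.3.3 is the section that sites and the sponsor work from: it describes announcing the closure of a subgroup once the desired number is reached. A team that takes ten as that number for VT could stop looking for further VT patients before the 7.2 target is met. Second, if the study ends with 10 or 11 VT recordings, the count meets 8.1.3.3 and the prose of 11.2 but misses 7.2, and the reasoning from 12 samples no longer applies to it.

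**Working it through.** **Inputs**
- Conditions: 14 in protocol 8.3.2, so 13 besides VT.
- Minimum for each other condition: 6 (7.2 and 11.2).
- VT minimum: 12 (7.2, SAP chapter 10, formula in 11.2) or 10 (8.1.3.3, prose of 11.2).
- Reference success rate: 50 %, with an exact 95 % confidence interval and a 5 % level (11.2). The two-sided level is from SAP 5.3.
- Non-evaluable recordings: 10 % (11.2).

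**1. The plan's own totals**

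Minimum = 13 × 6 + VT minimum; enrolled = minimum / (1 − 0.10).

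| VT minimum | Minimum total | Divided by 0.9 | Rounded up |
|---|---|---|---|
| 12 | 78 + 12 = 90 | 100.0 | 100 |
| 10 | 78 + 10 = 88 | 97.8 | 98 |

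Twelve reproduces the printed 90 and 100 exactly. Ten does not.

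**2. The plan's own significance statements**

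Two-sided p = 2 × P(X ≥ x) for X binomial with n samples and success rate 0.5. The lower limit is from the exact (Clopper-Pearson) 95 % interval.

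| Result | Calculation | p | Lower limit |
|---|---|---|---|
| 6 of 6 | 2 × 1/64 | 0.031 | 54.1 % |
| 10 of 12 | 2 × (66 + 12 + 1)/4096 = 2 × 79/4096 | 0.0386 | 51.6 % |
| 9 of 12 | 2 × 299/4096 | 0.146 | 42.8 % |
| 9 of 10 | 2 × (10 + 1)/1024 = 2 × 11/1024 | 0.0215 | 55.5 % |
| 8 of 10 | 2 × (45 + 10 + 1)/1024 = 2 × 56/1024 | 0.109 | 44.4 % |

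The statements for 6 of 6 and 10 of 12 both reproduce, and 10 is the smallest significant count among 12. Among 10 samples the smallest significant count is 9. A one-sided 5 % level gives the same cut-offs: 8 of 10 has a one-sided p of 0.055 and 9 of 12 of 0.073. So twelve samples tolerate two failures of an algorithm, and ten tolerate one.

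**3. Can the two numbers be reconciled by reading?**
- *Ten means the ten successes out of twelve.* No. The prose of 11.2 counts patients, and 8.1.3.3 separately counts inclusions.
- *Ten patients supply twelve samples.* No. The formula adds 12 to a count of patients.
- *Ten evaluable out of twelve enrolled.* No. The allowance for non-evaluable recordings is applied afterwards to the full 90, so VT would be inflated twice. Section 7.2 also sets twelve in the sentence that defines the endpoint as successful ECGs.

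**The case against.** The best case on the other side is that nothing has been miscalculated and little depends on the number. The sums of 90 and 100 are right, and so is the statement about 10 of 12. Section 11.2 says that a sample size calculation does not apply, 7.2 states no hypotheses, 11.4 has no pass/fail criterion, and SAP 1.1 makes no inferential analysis mandatory. The 10-of-12 sentence illustrates a later algorithm evaluation and is not an analysis of this study. SAP chapter 10 tabulates recordings by condition and does not compare them with a minimum, and the only VT minimum it mentions is twelve. Neither version caps VT, so no text requires closing the subgroup at ten. The planned 100 patients cover both versions.

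All of this stands as a limit on the consequence. This is an inconsistency between passages and not an error of calculation, and the p-values serve only to show which number the section was built on. The SAP excerpt is a copy of 7.2 and so does not add independent support for twelve. None of it removes the contradiction: the protocol gives two minimums for the same quantity, and the section that governs allocation and closure of subgroups carries the one that the formula does not use.

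**Conclusion.** The concern holds and is minor. The protocol sets the VT minimum at both twelve and ten, and no passage resolves it. The 10-of-12 rule, the + 12 in the formula, and the totals of 90 and 100 fit only twelve. The gap is two VT patients, which would also move the totals to 88 and 98. It matters only if the final VT count is 10 or 11; then the same count meets 8.1.3.3 and misses 7.2.

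The arithmetic assumes, as 11.2 indicates, exact binomial calculation against 50 % and inflation by division by 0.9. That twelve is the intended number is an inference from the formula, the rule and 7.2. Only the sponsor can confirm it.

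**What to change.** Change the VT minimum to twelve in 8.1.3.3 and in the prose of 11.2. Every passage then agrees, and 7.2, the SAP, the 90 and the 100 need no change. The cost is one number in each of two protocol sections. The sponsor has to decide under section 13 whether the correction counts as substantial.

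If ten is intended, more has to change: 7.2 and its excerpt in SAP chapter 10 to ten, the illustration in 11.2 to 9 of 10, and the formula to 13 × 6 + 10 = 88. The inflated figure would then be 98. The planned 100 could stay as a rounded-up number; if it is lowered, 11.2 and the sample size line of the synopsis must be changed together.

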11.3 Expected drop-out rate

It is expected that at least 10 % of the enrolled patients can only be partly included or not at all in the analysis of data, e.g. due to withdrawal of consent, refusal to participate in the Holter ECG or premature termination without documentation of the intended ECG pattern.

11.4 Pass/fail criteria

Not applicable.

11.5 Provision for an interim analysis

As there is no hypothesis to test, no comprehensive interim analysis is planned at a certain point in time. The acquired data will be continuously forwarded to the technical department for analysis.

11.6 Termination criteria

Not applicable

11.7 Procedures for reporting of deviations to the statistical plan

If deviations to the statistical plan become necessary for the clinical report, the changes and the reason(s) for the changes will be reported in the clinical report.

11.8 Specification of subgroups

There are no pre-defined sub-groups.

11.9 Procedure for accounting of all data for analysis

Due to the use of the electronic data capture and the required strict adherence to the monitoring plan, an adequate data acquisition of all data is ensured.

11.10 Handling of missing, unused and spurious data

Missing or spurious data will not be imputed.

11.11 Exclusion of data from confirmatory data analysis

In the following cases, data is to be excluded from analysis or prevented from inclusion into analysis:

- No data is allowed to be collected and included in the absence of a documented consent

Details are provided in the Statistical Analysis Plan.

11.12 Minimum and maximum number of patients per site

There is no maximum or minimum number of patients per site.

12 DATA MANAGEMENT

12.1 Data protection

According to corresponding national laws, the patient (or his or her legal representative) must declare in the Informed Consent Form (ICF) that he or she agrees to the recording of his or her medical data and their pseudonymized transfer to the sponsor, and, if necessary, to responsible Ethic Committee (EC) and Competent Authority (CA). The patient agrees that authorized personnel or designees of the sponsor and the involved EC or CA (if applicable) may gain insight in the patient file to ensure that the patient was adequately informed about the clinical investigation and that the clinical investigation plan was followed properly.

All patient-related data and information received from the clinical study will be handled confidentially. The collected data will be transmitted to the sponsor for electronic data processing, safety reporting and analysis in compliance with the data protection law. The data will be pseudonymized at the sites before transmission, without using patient initials, to ensure traceability of data, but preventing unauthorized identification of individual patients. All clinical data will be stored in a validated system environment with adequate protection against unauthorized access. Insight will be given to responsible EC and CA upon request.

All involved parties, including subcontractors, are bound to data privacy according to the applicable data protection law. All patients will be informed on all relevant regulations concerning data secrecy and data protection which are applicable for the BIO|CONCEPT. ECG-Library study in the patient informed consent form. Specifically, all patients will be educated about their rights concerning data access, data correction, and data deletion according to applicable legislation.

The patient identification log sheet, in which the patient ID code, name, date of birth and date of informed consent is entered, will remain at the investigational sites. No copies of the patient identification log sheet will be provided for the sponsor. The patients will be informed on the fact that exact identification of the patient is only possible for the investigator.

12.2 Data collection

All study-relevant patient data will be documented pseudonymously in electronic case report forms (CRF). The established Clinical Data Management System (CDMS) is 'iMedNet' of the vendor MedNet Solutions, Inc. As a pure internet-based application that is used with the current versions of current internet browsers, there is no specific local software to support (cloud based 'Software as a Service' SaaS). iMedNet supports industry standards (Regulation (EU) 2016/679 (incl. Corrigendum dated 23 May 2018), FDA 21 CFR Part 11 and HIPAA).

Use of the clinical data management system (CDMS) will allow 24 hours 7 days a week access to the module. The Principal Investigator (PI) as well as those co-investigators to whom the PI delegates data entry and authorization of CRFs needs to be trained on iMedNet. After appropriate documentation of the training, user access is granted. Site staff with user access will be directed to a page where they will enter their assigned user ID and password in order to access the system. Once these have been validated, there will be options for entering a new patient or new patient data into the system.

For the majority of the CRF entries, source data needs to be maintained at the site and will be collected in adequate files (e.g. patient files). The data have to be stored and shall be made available upon request in order to allow source data verification. Exceptions for which the CRF entry can be regarded as source data are indicated in the Monitoring plan or in the respective section of the CIP.

12.3 Procedures used for data review, CDMS cleaning, and issuing and resolving data queries

After data entry into the Clinical Data Management System (CDMS), the clinical data is automatically checked with programmed quality checks. Additionally, the CRF will be checked against source data by clinical monitors during periodic monitoring visits as described in the

Monitoring Plan. Errors, discrepancies, missing data, and entries out of range are resolved by automatically (CDMS) and manually (clinical monitor, clinical data manager) generated data queries and deviation forms.

The investigational site is obliged to answer all incoming data queries and deviation forms in due time to clarify the open issues. Corrections to the CRF can only be done by the designated site personnel and have to be signed by an authorized investigator approving thereby the completeness and correctness of the data. The CDMS supports detailed tracking of the query process since all changes are automatically recorded in the system's audit-trail.

Clarification of all open queries is a precondition for site closure in case of premature or regular study termination.

Prior to the final data analysis, all endpoint relevant data are checked for consistency and plausibility in a blinded way by the biostatistician.

12.4 Procedures for verification, validation and securing of electronic data systems

The Clinical Data Management System (CDMS) is hosted on a dedicated database server at the vendor MedNet Solutions, Inc. Only authorized users with fixed roles have access to the Clinical Data Management System (CDMS). The access is controlled and maintained by the Clinical Data Management. Every access is automatically logged and changes of the clinical data are stored in independent audit trails. The CDMS is verified and validated accordingly. The user interface and the internal business logic is validated accordingly and verified during the study related development and before release for data entry.

An authenticated user account is created and maintained by BIOTRONIK for each authorized user once the user has completed appropriate training. Users are obligated to keep their password confidential.

Depending on their role within the investigational study, users are limited to 'read only# or may be given permits to enter or update data, provide resolutions to queries and apply electronic signatures. Only investigators are allowed to sign the entries.

12.5 Data retention and archiving

All study related electronic documents are stored in the archive of BIOTRONIK which provides storage conditions free from risk of fire, flood, theft and vermin. The access to the files is controlled.

After CDMS closure, all CRF data and the audit trail and other relevant CDMS content are exported and stored electronically for at least 15 years on the archive server.

At the end of this period, requirements from laws and other regulations will be reconsidered in order to decide whether the retention period must be extended or data must be deleted.

All relevant study related documents have to be stored in the Investigator Site File. Documents containing patient's data, raw data and other study related documents have to be archived in the investigational site. In case of electronic source data (e.g. electronic patient files) adequate actions have to be taken to ensure data availability during the whole archiving period.

13 AMENDMENT PROCEDURES

If throughout the course of the study changes to the Clinical Investigation Plan (CIP) are deemed to be necessary, a change justification has to be prepared which includes the rationale and content of the adjustment. The modification of the CIP can either be summarized in a separate document as an attachment to the current applicable version of the CIP **or** result in a new version of the CIP.

If the changes have impact on study related procedures or data analysis they are substantial by definition.

New versions of the CIP or substantial amendments have to be reviewed and confirmed by the Coordinating Investigator. All principal investigators have to acknowledge the receipt of an amendment by either signing the CIP acknowledgement page which is part of the CIP, or by signing the amendment agreement form if no new CIP version was created.

Before implementation of any changes, substantial amendments have to be approved by the Ethics Committee (EC) and – if applicable – by the Competent Authority (CA). Non-substantial amendments are submitted for notification only.

The investigator should not implement any deviation from or changes to the CIP without agreement of the sponsor and prior review and documented approval from the EC (and CA if required). The only exception is the necessity to eliminate an immediate hazard to the subjects, or when the change involves only logistical or administrative aspects of the study.

14 DEVIATIONS FROM CLINICAL INVESTIGATION PLAN

14.1 CIP compliance and exceptions

All sponsor personnel, all investigational site personnel as well as other third parties, who are involved in tasks covered by this CIP, are generally obliged to comply with this CIP.

A **deviation** is any failure to follow, intentionally or unintentionally, the requirements of the CIP, including laws, guidelines and other regulation as far as required by the CIP and applicable laws, as well as applicable amendments. Deviations that are likely to seriously affect or that actually have seriously affected the rights or safety or wellbeing of subjects or the scientific integrity of the clinical investigation are **major** deviations. Otherwise they are **minor** deviations.

Erroneous, spurious or missing data in a CRF is not a deviation in itself and is handled according to the query processes described in the data management section of this CIP. However, the underlying reason might be a deviation.

Under **emergency** circumstances, deviations from the CIP to protect the rights, safety and well-being of human subjects may proceed without prior approval of the sponsor and the ethics committee.

No waivers from the CIP are allowed.

14.2 Recording, reporting and analyzing deviations

All deviations are recorded and reported electronically in the CDMS system iMedNet. If the CRF logic has detected a CIP deviation based on the data entry, deviation forms are triggered automatically by iMedNet. Additionally, deviation forms can be created manually via iMedNet by the site or by the sponsor personnel.

14.2.1 Site specific deviations

Investigational sites are obliged to record any deviation immediately as they become aware of it. In addition, compliance to the CIP is verified by the sponsor through monitoring visits. Each site specific deviation is assessed for the need of corrective or preventive actions.

